5.5.1 Study Discontinuation and Closure

This study may be temporarily suspended or prematurely terminated if there is sufficient

reasonable cause. If the study is prematurely terminated or suspended, the Principal Investigator will promptly inform study participants and the IRB and will provide the reason(s) for the termination or suspension. Study participants will be contacted, as applicable, and be informed of changes to study visit schedule.

Circumstances that may warrant termination or suspension include, but are not limited to:

- Determination of unexpected, significant, or unacceptable risk to participants
- Demonstration of efficacy that would warrant stopping
- Insufficient compliance to protocol requirements
- Data that are not sufficiently complete and/or evaluable
- Determination that the primary endpoint has been met
- Determination of futility

The Study may resume once concerns about safety, protocol compliance, and data quality are addressed, and satisfy the IRB and/or Food and Drug Administration (FDA).

5.6 Duration of Follow-Up

Patients will be followed for 30 days after the last dose is administered or until one of the following occurs: patient enrolls on another protocol, patient receives standard of care, or death, whichever comes first. The follow-up will consist of a phone call between Days 27-30 after the last dose to evaluate adverse events that were ongoing and any new events that might be deemed related to the therapy. Any patients with unresolved toxicity \geq Grade 2 at the time of the post-study clinical follow-up visit will be followed with clinic visits or phone calls as appropriate until resolution of the toxicity to less than Grade 2 or stabilization of the toxicity.

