5.7 Criteria for Removal from Study

Patients will be removed from study for one of the following reasons: completed 30-day follow up period or toxicities are unresolved but stabilized, patient enrolls on another protocol, or patient receives standard of care. The reason for study removal and the date the patient was removed must be documented in the medical record and communicated to Central Registration per Section 4.

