9.3.3 Expedited Reporting Guidelines

Use the NCI protocol number and the protocol-specific patient ID assigned during trial registration on all reports.

Note: A death on study requires both routine and expedited reporting, regardless of causality. Attribution to treatment or other cause must be provided.

Death due to progressive disease should be reported as **Grade 5 “Disease progression”** in the system organ class (SOC) “General disorders and administration site conditions.” Evidence that the death was a manifestation of underlying disease (e.g., radiological changes suggesting tumor growth or progression; clinical deterioration associated with a disease process) should be submitted.

Phase 1 and Early Phase 2 Studies: Expedited Reporting Requirements for Adverse Events that Occur on Studies under an IND/IDE within 30 Days of the Last Administration of the Investigational Agent/Intervention ^{1, 2}

FDA REPORTING REQUIREMENTS FOR SERIOUS ADVERSE EVENTS (21 CFR Part 312)

NOTE: Investigators **MUST** immediately report to the sponsor (NCI) **ANY** Serious Adverse Events, whether or not they are considered related to the investigational agent(s)/intervention (21 CFR 312.64)

An adverse event is considered serious if it results in **ANY** of the following outcomes:

- 1) Death
- 2) A life-threatening adverse event
- 3) An adverse event that results in inpatient hospitalization or prolongation of existing hospitalization for \geq 24 hours
- 4) A persistent or significant incapacity or substantial disruption of the ability to conduct normal life functions
- 5) A congenital anomaly/birth defect.
- 6) Important Medical Events (IME) that may not result in death, be life threatening, or require hospitalization may be considered serious when, based upon medical judgment, they may jeopardize the patient or subject and may require medical or surgical intervention to prevent one of the outcomes listed in this definition. (FDA, 21 CFR 312.32; ICH E2A and ICH E6).

ALL SERIOUS adverse events that meet the above criteria **MUST** be immediately reported to the NCI via electronic submission within the timeframes detailed in the table below.

Hospitalization	Grade 1 and Grade 2 Timeframes	Grade 3-5 Timeframes
Resulting in Hospitalization \geq 24 hrs	10 Calendar Days	24-Hour 5 Calendar Days
Not resulting in Hospitalization \geq 24 hrs	Not required	

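### A patient who moves to other therapy on days 1 to 26 after the last dose has no scheduled safety follow-up contact within the 30-day reporting window

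*Combined protocol and SAP*

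**What the plan says.** Four parts of the protocol bear on this.

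- **Section 5.6** sets the length of follow-up: "Patients will be followed for 30 days after the last dose is administered or until one of the following occurs". The events that end it early are: "patient enrolls on another protocol, patient receives standard of care, or death, whichever comes first". It then fixes the content: "The follow-up will consist of a phone call between Days 27-30 after the last dose". That call covers adverse events still open and new ones that might be related to treatment. Patients with unresolved toxicity of Grade 2 or higher are followed for longer, but this is assessed "at the time of the post-study clinical follow-up visit".
- **Section 5.7** removes a patient from study on completing the 30 days, when unresolved toxicity has stabilized, or on either therapy event: "patient enrolls on another protocol, or patient receives standard of care".
- **Section 5.8** says that a patient who stops because toxicity has not resolved within the permitted two-week delay is followed until it does. It mentions no cut-off at new therapy.
- **Section 9.3.3** covers adverse events "within 30 Days of the Last Administration of the Investigational Agent/Intervention" and requires investigators to report any serious adverse event to the sponsor, related or not.

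The Section 10 calendar runs from screening to cycle 3 onwards. It has no end-of-treatment or post-treatment column.

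**The concern.** The follow-up period and the reporting window are both 30 days, so on paper they match. They come apart because the single planned contact sits at the end of the period, while the events that close the period can happen at any time before it. Whenever one of those events comes first, the call is no longer due.

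This is a first-in-human trial whose primary objective is safety, tolerability and the recommended phase 2 dose. Patients who come off drug for progression or toxicity are plausibly the ones who move soonest to something else. Safety information lost this way is therefore unlikely to be missing at random, and the late-event profile could look cleaner than it is. The clause meant to protect patients with open toxicity has its own defect: its trigger is a visit the protocol never schedules.

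**Working it through.** The plan gives no figure to reproduce. The check is a timeline comparison.

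**1. Inputs.** Follow-up lasts 30 days unless cut short (5.6). It is cut short by another protocol, standard of care or death (5.6), and the two therapy events also remove the patient (5.7). One call is planned, on days 27 to 30 (5.6). The expedited reporting window is 30 days (9.3.3).

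**2. Scheduled contacts by start day.** Let d be the day after the last dose on which the therapy event occurs.

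| d | Scheduled follow-up contacts in the 30-day window |
|---|---|
| 1 to 26 | 0 (participation ends before the call window opens) |
| 27 to 30 | 0 or 1, depending on whether the call was already made |
| after 30 | 1 |

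So 26 of the 30 possible start days cancel the only planned contact.

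**3. What other visits could fill the gap.** In a full cycle the last dose is on cycle day 25 (Appendix D). If the next cycle is due on day 29, its examination and laboratory tests may be done up to 3 days early (Section 10), that is on days 26 to 29. This is 26 − 25 = 1 to 29 − 25 = 4 days after the last dose. A patient found to have progressed around then may be seen once after dosing has ended. That visit is not designated as safety follow-up, is not assured for someone who stops mid-cycle, and reaches only the first few days of the window.

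**4. The provisions for unresolved toxicity, side by side.**

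- 5.6 extends follow-up for Grade 2 or higher toxicity, judged at a clinical visit. The same section plans only a call, and the calendar shows no such visit.
- 5.8 follows patients who stopped because toxicity did not resolve. It does not cover those who leave for progression, withdrawal or another reason.
- 5.7 removes the patient on new therapy with no exception for open toxicity. For a patient covered by 5.8 who then starts other therapy, the two sections give different answers.

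**5. Scale.** The documents give no rate of early transfer to other therapy. Assumption only: 10% of the 40-patient accrual ceiling is 0.10 × 40 = 4, and 50% is 0.50 × 40 = 20. Section 8.2 puts the maximum evaluable number at 33, so these counts are on the high side as a base.

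**The case against.** The case on the other side has real content.

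- **The reporting duty does not lapse.** 9.3.3 applies whatever treatment the patient is on, and related serious events remain reportable after day 30. This stands. What is missing is a scheduled prompt, and under-counting is inferred rather than shown.
- **Some patients are covered.** A reader might infer that unresolved drug-related toxicity is simply lost at new therapy. The documents do not support that: 5.8 requires follow-up to resolution for patients stopped on that ground, and 5.7 itself lists stabilized toxicity as a reason for removal. What remains is a conflict between 5.7 and 5.8, and no cover for patients who leave for other reasons.
- **A visit may occur anyway.** A reader might also infer that these patients have no safety contact at all after treatment. That is too strong, given the pre-cycle and restaging visits; the claim is confined to scheduled follow-up.
- **Early transfer may be uncommon.** The 1-week minimum in 3.1.2 suggests that a next trial could enrol on day 7, leaving 30 − 7 = 23 days unobserved. But 1 week is the floor of a rule that otherwise asks for 4 weeks or, if known, 5 half-lives, whichever is shorter. With the half-life unknown, the rule gives day 28, inside the call window. It also governs entry to this trial, not to others or to standard care. The 23-day case is not typical and is not relied on here.
- **New therapy confounds attribution.** True, but this argues for a contact before the new therapy starts rather than for none.

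**Conclusion.** The point holds as a gap in scheduled safety follow-up. If other therapy begins on days 1 to 26, the protocol plans no contact within the 30 days that 9.3.3 covers. The unresolved-toxicity provisions do not reliably close the gap, because one depends on an unscheduled visit and another is not reflected in 5.7. This follows from the text and needs no assumption. The number of patients does: 4 to 20 is an illustration under an assumed 10% to 50%.

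A reader might go further and infer that dose decisions are compromised. The documents do not support that. Dose-limiting toxicity is judged on cycle 1, which has weekly examinations and laboratory tests, so for patients who complete cycle 1 the gap does not enter the escalation rule. What it weakens is the description of late and post-treatment events. It is worth correcting because the correction is cheap and the loss is unlikely to be random.

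**What to change.** 1. In 5.6 and 5.7, state that the safety call is made on days 27 to 30 or before the first dose of other therapy, whichever comes first. Since 5.6 and 5.7 act on enrolment in another protocol, which may precede its first dose, say that the call is still owed at that point.
2. In 5.7, state that reporting of serious adverse events to day 30 under 9.3.3 continues after removal.
3. Reconcile 5.6, 5.7, 5.8 and the Section 10 calendar on two matters: the clinical visit that 5.6 refers to but nothing schedules, and how unresolved Grade 2 or higher toxicity is followed once other therapy begins.

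The cost is wording, plus an earlier call for some patients. Serious events collected after new therapy starts will be harder to attribute and should be reported with that caution. No new laboratory monitoring is needed to close the gap.

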5.7 Criteria for Removal from Study

Patients will be removed from study for one of the following reasons: completed 30-day follow up period or toxicities are unresolved but stabilized, patient enrolls on another protocol, or patient receives standard of care. The reason for study removal and the date the patient was removed must be documented in the medical record and communicated to Central Registration per Section 4.

5.8 Dosing delays

Doses of CB-5339 will be held or modified only for adverse events that are felt to be at least possibly related to study drug. Treatment may be delayed for a maximum of 2 weeks for resolution of toxicities; in case toxicities do not resolve as defined below, the patient will not receive further therapy on this protocol and will be followed for resolution of toxicities. Dose modifications are intended for within-cycle and start of next cycle changes. If administration of CB-5339 is interrupted for any reason, it will not be made up, and counting of the cycle days will continue.

Patients will be allowed up to 2 dose reductions. For patients on dose level 1, the dose will be reduced to dose level -1 (25 mg/day; 3 days on/4 days off each week q 28-day cycles). Patients

who require a dose reduction will not have the dose re-escalated.

Treatment may be delayed for a maximum of 1 day during a cycle due to unavoidable scheduling conflicts.

5.9 Dose Modifications

- 5.9.1 Grade 2 drug-related toxicity: therapy will not be interrupted for Grade 2 toxicities with the exception of ocular toxicity.
- 5.9.2 Grade 3-4 drug-related non-hematologic toxicities: CB-5339 will be held until toxicities recover to \leq grade 1 or baseline (with the exception of alopecia) prior to re-initiating therapy at the next lower dose level. Electrolyte abnormalities will not require dose reduction if resolution to grade 1 or less is documented within 48 hours. Dose modifications for nausea, vomiting, and diarrhea will be made only if they are refractory to treatment (refer to Section 5.4). Diarrhea, nausea, and vomiting that fail to resolve to \leq Grade 2 within 24 hours despite adequate medical management are considered refractory.
- 5.9.3 Grade 3 hematologic toxicities: drug will be held for grade 3 hematologic toxicities, except leucopenia in the absence of neutropenia or lymphopenia, until resolution of toxicity to at least a grade 1 or baseline. Dose modification for grade 3 hematologic toxicity will be made only if the patient has recurrent grade 3 hematologic toxicity despite appropriate supportive care, e.g., growth factors; those experiencing recurrent grade 3 hematological toxicity despite optimal management may be dose reduced to the lower dose level.
- 5.9.4 Grade 4 drug-related hematologic toxicities of thrombocytopenia and neutropenia: CB-5339 will be held until toxicities recover to \leq grade 1 and therapy re-initiated at the next lower dose level. Agent will not be held or dose modified for leucopenia in the absence of neutropenia or lymphopenia.
- 5.9.5 All patients with grade 4 cardiac, respiratory, or neurologic toxicities at least possibly attributable to the investigational drug will be taken off treatment.

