Labs (CBC with differential; serum chemistries) will be performed at baseline (within 8 days of the start of protocol therapy), during weeks 1, 2, 3, and 4 of cycle 1, and at the start (+/- 1 day during the cycle and up to 3 days before start of a new cycle) and during week 1 of every cycle thereafter. For the first three patients enrolled on the study who will receive their initial week of treatment as inpatients, labs will also be performed on Cycle 1 Day 2 prior to CB-5339, on Day 3 based on the result from Day 2, on Day 4 prior to CB-5339, on Day 6 (Sunday at the Day Hospital), and on Day 8 (C1W2).

ECG will be performed at baseline (within 8 days of the start of protocol therapy) and will be

performed on day 1 pre-dose and at 2 hours post dose/the time to peak concentration of every subsequent cycle, and as clinically indicated.

Blood and urine samples for correlative PD and PK studies will be collected from all patients as described in [Section 7](#).

Paired tumor biopsies will be collected at baseline and then 4-6 hours after receiving the first dose in the expansion cohort; an optional biopsy may be collected at disease progression or “pre-progression” (defined as a 10-19% increase in tumor volume as shown on a restaging scan).

NEI associate investigators will perform an ophthalmology examination that includes optical coherence tomography (OCT), color vision testing, and a questionnaire on all patients during screening. The questionnaire will be repeated after treatment on cycle 1 day 1 or 2; the questionnaire and eye examinations can be repeated by NEI as clinically indicated. Details about the questionnaire and eye examinations can be found in [Appendix B](#) along with thresholds for pre-existing visual impairment. Patients should be encouraged to report any vision changes to the study team immediately.

CB-5339 is administered orally on a schedule of once daily, 4 days on and 3 days off (28-day cycle). Dose escalation will continue until the RP2D (MTD) is established. Intra-patient dose escalation will be permitted; refer to Section 5.2 regarding conditions for permitted intra-patient dose escalation.

Dose Escalation Schedule	
Dose level	Dose of CB-5339 (mg/day, once daily 4 days on/3 days off weekly)
-1	25 mg/day; 3 days on/4 days off
1 (starting)	25
2	50
3	100
4	150
5	225
6	300

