5.2 Definition of Dose-Limiting Toxicity

Determination of dose-limiting toxicity (DLT) will be based on toxicities observed in the first cycle of therapy and felt to be at least possibly related to study drug. A greater than 2-week delay for AEs before cycle 2 would be considered a DLT.

This study will follow design 3 of the Simon accelerated titration designs (Simon et al., 1997). We will accrue to the next dose level only after we have established safety at lower dose levels.

During this accelerated phase, there will be one patient per dose level. After the first instance of a drug-related Grade 2 toxicity (during the first cycle) at any dose level, the accelerated phase will end, and dose escalation will be changed to a 3 + 3 design. All decisions on dose expansion and DLT will be made on the first cycle of treatment.

When the accelerated phase ends, the trial will go back to a traditional 3+3 design. That is, additional patients will be placed on the dose level at which the last new patient was treated; 3 patients will be treated initially at each new dose level.

Number of Patients with DLT at a Given Dose Level	3+3 Escalation Decision Rule
0 out of 3	Enter 3 patients at the next dose level.
≥ 2	Dose escalation will be stopped. This dose level will be declared the maximally administered dose (highest dose administered). Three (3) additional patients will be entered at the next lowest dose level if only 3 patients were treated previously at that dose.
1 out of 3	Enter at least 3 more patients at this dose level. 
• If 0 of these 3 patients experience DLT, proceed to the next dose level.• If 1 or more of this group suffer DLT, then dose escalation is stopped, and this dose is declared the maximally administered dose. Three (3) additional patients will be entered at the next lowest dose level if only 3 patients were treated previously at that dose.
≤ 1 out of 6 at highest dose level below the maximally administered dose	This is generally the recommended phase 2 dose. At least 6 patients must be entered at the recommended phase 2 dose.

If ≥ 2 patients experience DLT on dose level -1, the study will be placed on hold and all data reviewed to make a decision about further evaluation of the study drug.

DLT is defined as an adverse event that is related (possibly, probably, or definitely) to

administration of study drug and fulfills one of the following criteria:

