- 5.2.1 Inability to administer $\geq 75\%$ of doses of study drug in the absence of toxicity unless due to patient non-compliance.
- 5.2.2 Any treatment-related death
- 5.2.3 All \geq Grade 3 toxicities, with the exceptions noted below.

The following toxicities are NOT considered as DLTs:

- 5.2.4 Alopecia
- 5.2.5 Grade 3 fatigue, asthenia, anorexia, or constipation
- 5.2.6 Grade 3 nausea, vomiting, or diarrhea not requiring hospitalization, tube feeding, total parenteral nutrition, or prolonged hospitalization
- 5.2.7 Grade 3 alkaline phosphatase (ALP) or lactate dehydrogenase (LDH)
- 5.2.8 Grade 3 bilirubin elevation that is asymptomatic, returns to \leq Grade 2 levels in ≤ 7 days, and is not related to liver pathology (i.e., predominantly indirect bilirubin, Gilbert's syndrome)
- 5.2.9 Grade 3 electrolyte abnormality that improves to \leq Grade 1 after 48 hours with appropriate management.
- 5.2.10 Any degree of leukopenia or lymphopenia (except when associated with grade 4 neutropenia that lasts > 5 days) will not be considered dose limiting
- 5.2.11 Grade 3 or 4 neutropenia or thrombocytopenia lasting < 5 days

Aspartate aminotransferase (AST) or alanine aminotransferase (ALT) $\geq 3 \times$ upper limit of normal (ULN) with total bilirubin $\geq 2 \times$ ULN, alkaline phosphatase $< 2 \times$ ULN (FDA "Hy's Law") would be considered a DLT when determined to be related to study drug. Any other toxicity considered relevant by the investigator may be considered a DLT after discussion with CTEP.

Intra-patient dose escalation will be permitted if: **a**) there is no toxicity $>$ Grade 1 that is related (possibly, probably, or definitely) to the study drug at the initial dose level experienced by that patient, **b**) higher doses have been evaluated and completed without DLT, and **c**) the patient's disease is either stable or has progressed. Doses may be escalated, provided conditions a-c are met, up to the last evaluated dose level NOT associated with DLT.

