5.5 Duration of Therapy

In the absence of treatment delays due to adverse event(s), treatment may continue until one of the following criteria applies:

- Disease progression
- Intercurrent illness that prevents further administration of treatment
- Significant toxicity occurs despite 2 dose reductions or no lower dose level exists,
- Patient decides to withdraw from the study
- General or specific changes in the patient's condition render the patient unacceptable for further treatment in the judgment of the investigator
- Patient non-compliance
- Pregnancy
- Termination of the study by sponsor
- The drug manufacturer can no longer provide the study agent

The reason(s) for protocol therapy discontinuation, the reason(s) for study removal, and the corresponding dates must be documented in the Case Report Form (CRF).

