10. STUDY CALENDAR

Baseline history, physical examination, laboratory evaluations, and ECG must be conducted within 8 days prior to start of protocol therapy. If protocol therapy is started within 8 days of the eligibility screening evaluations (see [Section 3.4](#)), the results from these screening evaluations may be used as baseline measurements. If > 8 days have passed since the screening evaluations, the medical history, physical examination, laboratory evaluations, and ECG must be repeated prior to starting protocol therapy. Baseline tumor imaging must be performed within 28 days prior to start of protocol therapy. If protocol therapy is started within 28 days of the eligibility screening tumor imaging, the screening evaluation imaging results may be used as baseline measurements; if > 28 days have passed since the screening evaluation tumor imaging, the imaging must be repeated prior to starting protocol therapy.

Start of next cycle may be delayed for up to 1 week to accommodate scheduling conflicts. Treatments within a cycle may be delayed up to +/- 1 day to accommodate scheduling conflicts. History and physical examination and laboratory evaluations can be performed up to 3 days before the start of the next cycle. The research team may perform additional safety/monitoring tests as clinically indicated.

The first three patients will be admitted to the NIH Clinical Center for 5 days of in-patient evaluation followed by out-patient evaluation at the day hospital on days 6 and 7. Monitoring (vital check, PO₂, serum chemistries, and CBC) will be enhanced for these patients based on their clinical status (see chart)

	Pre-Study Eligibility Screening	Baseline Clinical Evaluation	Cycle 1				Cycle 2				Cycle 3 onwards
			Wk 1	Wk 2	Wk 3	Wk 4	Wk 1	Wk 2	Wk 3	Wk 4	
CB-5339 ^a			X	X	X	X	X	X	X	X	
Informed consent	X										
Demographics	X										
Med. History	X	X ^j					X				prior to treatment
Physical exam ^b	X	X ^j	X	X	X	X	X				prior to treatment
ECG ^b	X	X ^j					X				X
Urinalysis	X	X ^j					X				
Height and Weight	X	X ^j					X				X
Performance Status	X	X ^j	X	X	X	X	X				X
CBC w/diff, plts ^c	X	X ^j	X	X	X	X	X				X
Serum chemistry ^c	X	X ^j	X	X	X	X	X				X
Tumor Measurement ^d	X	X ^j									X
B-HCG ^e	X	X ^j					X				prior to treatment
PK blood and urine ^f			X								
Blood samples for ctDNA ^h			X				X				start of every cycle
Blood samples for PBMCs ^g			X								
Ophthalmic Exam/ Questionnaire ⁱ	X		X								
ECHO ^j	X										

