Adverse event evaluation					X.....						X

a. CB-5339 will be given once daily for 4 consecutive days followed by 3 days without drug (QD4/3-off weekly for 4 weeks in consecutive 28-day cycles as specified in the dose escalation table. Drug is to be taken with water on an empty stomach, either 1 hour before or 2 hours after meals. Patients 1-3 will be admitted to the NIH Clinical Center for 5 days of in-patient evaluation followed by out-patient evaluation at the day hospital on days 6 and 7 (vital check, PO₂, serum chemistries, CBC). These first three patients will then resume treatment at the NIH Clinical Center on D8 (C1, Wk2) as outpatients.

b. For patients enrolled on the study after the the first three subjects, physical examination including vital signs and O₂ saturation level (pulse oximeter) will be conducted pre-study, during weeks 1, 2, 3, and 4 of cycle 1, and then at the start of every cycle thereafter (within 3 days prior to treatment). ECG will be performed at baseline (within 8 days of the start of

protocol therapy) and will be performed on day 1 pre-dose and at 2 hours post dose/the time to peak concentration of every subsequent cycle, and as clinically indicated.

Serum chemistries (sodium, potassium, chloride, bicarbonate, BUN, creatinine, glucose, AST, ALT, bilirubin, calcium, phosphorous, albumin, magnesium, alkaline phosphatase, LDH (with uric acid for patients with lymphoma only) and CBC with differential and platelets will be performed pre-study; for patients 1-3 at the following times during week 1: day 2 prior to CB5339, Day 3 as needed based on the result from Day 2, Day 4 prior to CB5339, Day 6 prior to CB-5339, then Cycle 1 week 2 (Day 8) , during weeks, 2, 3, and 4 of cycle 1, and then at the start (within 3 days prior to treatment) during week 1 of every cycle thereafter. Patients 4 onwards will have serum chemistries performed pre-study and then during weeks 1, 2, 3, and 4 of cycle 1, and then and at the start (within 3 days prior to treatment) during week 1 of every cycle thereafter.

- c. Radiologic examination will be performed at baseline and then every 2 cycles (3 cycles for patients on study for more than one year, 4 cycles for those on study more than 3 years).
- d. Urine pregnancy test (women of childbearing potential) will be conducted within 24 hours prior to CB-5339 administration at baseline, and within 24 hours prior to CB-5339 at the start of each cycle thereafter.

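### A drug-related Hy's Law liver pattern is a cycle 1 DLT at any grade, but section 5.9 requires no hold for it when both components are below Grade 3

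*Combined protocol and SAP*

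**What the plan says.** **DLT definition.** After the list of toxicities that are not DLTs, section 5.2 adds a liver paragraph. AST or ALT at or above 3 times ULN, with total bilirubin at or above 2 times ULN and ALP below 2 times ULN, "would be considered a DLT when determined to be related to study drug". The thresholds are multiples of ULN, and no grade is attached. DLT determination "will be based on toxicities observed in the first cycle of therapy". In the expansion cohort, section 5.3 continues to watch for events of DLT type after cycle 1.

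**Dosing rules.** Section 5.9 is organised by grade and by type of event. For Grade 2 drug-related toxicity, 5.9.1 says "therapy will not be interrupted for Grade 2 toxicities with the exception of ocular toxicity". The non-hematologic hold and dose reduction in 5.9.2 begin at Grade 3. There is no liver clause, and no rule that a DLT triggers a hold. Section 5.8 says that doses "will be held or modified only for adverse events that are felt to be at least possibly related to study drug" and leaves the resolution criteria to the text below it. Section 5.5 lets treatment end when changes in the patient's condition "render the patient unacceptable for further treatment in the judgment of the investigator". Section 5.10 gives eye events their own rules for holding and resuming, with CTEP medical monitor approval.

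**Chemistry schedule.** Draws are made in each of the four weeks of cycle 1. For later cycles, section 5 allows the start-of-cycle draw "up to 3 days before start of a new cycle) and during week 1 of every cycle thereafter". The section 10 footnote reads "at the start (within 3 days prior to treatment) during week 1 of every cycle thereafter". Section 10 adds: "The research team may perform additional safety/monitoring tests as clinically indicated".

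**The concern.** The protocol treats this liver pattern as serious enough to count against a dose level. Yet the section that tells the investigator what to do with the next capsule does not mention it, and its Grade 2 rule says not to interrupt. An investigator who follows 5.9.1 literally continues dosing through the pattern; one who holds drug departs from the text unless the event is recorded as Grade 3 or higher.

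This is a safety question for the individual patient in a first-in-human trial. It does not alter the escalation rule, the sample size or any error rate.

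**Working it through.** **1. The rules side by side.** Take a drug-related event that meets the 5.2 liver pattern with AST/ALT and bilirubin both below Grade 3.

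| Section | What it does with this event |
|---|---|
| 5.2 | Counts it as a DLT if it occurs in cycle 1 |
| 5.9.1 | Does not interrupt therapy for Grade 2, unless ocular |
| 5.9.2 | Does not apply; starts at Grade 3 |
| 5.8 | Event qualifies as one for which drug may be held, but no hold is required |
| 5.5 | Investigator may end treatment; not required, and no resumption rule |
| 5.10 | Eye events only |

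No row requires a hold.

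**2. Which values fall in the gap.** Section 9.2 names CTCAE 5.0 for adverse event reporting but does not print its liver cut-points, so they enter as an assumption. Let Grade 3 start above A times ULN for AST/ALT and above B times ULN for bilirubin. The gap is AST/ALT from 3 to A with bilirubin from 2 to B, and ALP below 2 times ULN.

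- Assumed CTCAE 5.0, normal baseline (A = 5, B = 3): AST/ALT 3 to 5 with bilirubin 2 to 3 times ULN.
- Lower cut-points (A = 4, B = 2.5): 3 to 4 with 2 to 2.5 times ULN.
- The gap closes only if A is 3 or less, or B is 2 or less.

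Section 3.1.6 admits AST/ALT up to 3 times ULN and bilirubin up to 1.5 times ULN. If grades are read relative to a raised baseline, A and B change and so does the zone. The documents do not settle this.

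**3. Doses between scheduled draws.** Dosing days in a cycle are 1–4, 8–11, 15–18 and 22–25, so 4 × 4 = 16 doses.

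From cycle 2, under section 5, take both draws as pre-dose, with the start draw on day 1 or in the three days before. If the week 1 draw is on day d, the doses before it are min(d − 1, 4), and the doses from it to the next start draw are 16 − min(d − 1, 4).

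| Week 1 draw | Doses since start draw | Doses to next start draw |
|---|---|---|
| Day 1 (start draw taken earlier) | 0 | 16 |
| Day 2 | 1 | 15 |
| Day 3 | 2 | 14 |
| Day 4 | 3 | 13 |
| Days 5–7 | 4 | 12 |

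Days 26–28 are off days, so a next start draw on any of them gives the same counts. The plus or minus 1 day allowance in section 5 is left out; it could shift a count by about one dose. If the section 10 footnote is read as one pre-dose draw per cycle, the interval is again 16.

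In cycle 1, weekly draws on the same weekday are 4 doses apart. No day is fixed within the week, so the span is 0 (day 5, then day 8 pre-dose) to 8 (day 1 pre-dose, then day 12). The first three patients have extra week 1 draws, which shorten this.

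**4. Which cycles.** The mismatch with 5.2 is a cycle 1 matter. Later, an escalation patient's event is no longer a DLT, and the reason for a hold is patient safety alone.

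**The case against.** **Different purposes.** Section 5.2 decides what counts for escalation; 5.9 directs individual dosing. They need not match, and elsewhere they do not: Grade 3 fatigue is not a DLT but falls under the 5.9.2 hold. This stands, so a mismatch alone would not be a fault. The fault is the missing safety action for this particular pattern.

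**Role of the liver paragraph.** It follows exceptions for Grade 3 ALP or LDH (5.2.7) and certain Grade 3 bilirubin rises (5.2.8), and may be there to override them. A reader might infer that it was written specifically to capture events below Grade 3; the documents do not establish that intent. It still carries no grade limit, so it reaches those events as worded.

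**Ways to hold drug.** A reader might infer that the protocol forbids a hold. It does not. Section 5.8 contemplates holds for related events without naming a grade, 5.5 allows stopping on judgment, and nothing says how a composite liver event is graded, so recording one Grade 3 event is not shown to be misgrading. These routes make continued dosing of a recognised case unlikely, but none is mandatory. The calls with the CTEP Medical Officer in section 12.1, at least monthly, help detection but set no dosing action.

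**Weak signal.** The listed ALT increase comes from CB-5083 patients (section 9.1.1). With CB-5339, rats showed minimally higher ALT that reversed (section 2.2.4), and no bilirubin signal is reported. This limits the expected frequency.

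**Conclusion.** The gap is real and narrow. When the 5.2 liver pattern is met, is drug-related and has both components below Grade 3, section 5.9 requires no hold, and its Grade 2 rule points to continued dosing.

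That such events exist depends on the CTCAE 5.0 cut-points, which are cited but not printed; it fails only if Grade 3 begins at or below 3 times ULN for AST/ALT or 2 times ULN for bilirubin. Under the assumed cut-points and a normal baseline, the zone is 3 to 5 with 2 to 3 times ULN.

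The interval of up to 16 doses from cycle 2 measures the spacing of scheduled draws. A reader might take it as the number of doses a patient would receive after the pattern is recognised. The documents do not support that, since as-indicated tests and investigator judgment can intervene. Nor do the dose counts carry the finding: while repeat values stay below Grade 3, 5.9 still requires no hold.

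No incidence is given, and few of at most 40 patients are likely to be affected. It should be fixed because the consequence could be serious and the change is small.

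**What to change.** In 5.9.1, list the liver pattern defined in 5.2 as an exception beside ocular toxicity.

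In 5.9, add that CB-5339 is held in any cycle when the pattern is met and is at least possibly related to study drug, whatever the component grades. Treatment is then either discontinued, or resumed at the next lower dose level only if all of these hold:

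- recovery to Grade 1 or less, or to baseline (the 5.9.2 threshold);
- recovery within the 2-week limit in 5.8;
- CTEP medical monitor approval, as 5.10 requires after eye events.

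State that this safety rule is separate from DLT counting.

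The cost is one exception clause and a short added rule. No new test is needed, since AST, ALT, ALP and bilirubin are already in the scheduled chemistry panel. The downside is that a few patients may have doses held who would otherwise have continued.
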